6.1 Analysis Sets

The ITT analysis set is henceforth referred to as the Full Analysis Set (FAS) and defined as follows:

 Full Analysis Set (FAS): Participants who were randomized within RGE plus placebo participants from regimens A-D who had an opportunity to complete placebo-controlled follow-up, classified according to their randomized treatment assignment. Participants who discontinue study drug but remain in the study will be included in the FAS. Observations completed after regimen data lock are excluded. Participants determined to not meet ALS diagnostic criteria are excluded.

The definition of the STF analysis set is revised as follows:

• Safety Full (STF) Set: Participants who initiated treatment within RGE plus placebo participants from regimens A-D who are not known to be ineligible for RGE and who initiated treatment in their respective regimen, classified according to the treatment they actually received. Observations made after premature permanent discontinuation of study drug are included in this sample, should such participants remain on study. Observations completed after regimen data lock are excluded.

An analysis set restricting shared placebo participants to those regimens in which study drug is administered by the same route as RGE is defined as follows:

• Efficacy Common Mode of Administration (ECM) Set: The subset of participants in the FAS who are in regimens in which study drug is administered by the same route as RGE.

The definitions of the ECC, ERO, STN, and SRO analysis sets are the same as described in the M-SAP with reference to the ITT analysis set now referencing the FAS analysis set.

• Efficacy Per-protocol (EPP) Set: The subset of participants in the FAS analysis set who initiated study treatment and who were not involved in protocol deviations related to eligibility, treatment, follow-up, assessment, or use of other disease-modifying treatments for ALS, classified according to the treatment they actually received. Final specification of participants included vs. excluded from the EPP analysis set will be defined prior to data lock. Inclusion or exclusion from the EPP analysis set of any participant for whom treatment

assignment was unblinded prior to data lock will be governed by the prespecified criteria above. If a participant's data are truncated for inclusion in the EPP analysis set due to a time-dependent event (e.g., non-adherence to protocol-specified dosing, initiation of a prohibited medication, initiation of edaravone, riluzole, or sodium phenylbutyrate/taurursodiol), clinical events observed up to 28 days after the censoring event will be included in the EPP analysis set. Data from placebo participants shared from other regimens will not be truncated due to non-adherence to protocol-specified dosing.

An analysis set that excludes participants who used sodium phenylbutyrate/taurursodiol during their follow-up for the placebo-controlled period is defined as follows:

• Efficacy Relyvrio Free (ERF) Set: The subset of participants in the ERO who were not using sodium phenylbutyrate/taurursodiol at baseline and did not start using sodium phenylbutyrate/taurursodiol after baseline and prior to completion of their Week 24 visit or death, earlier termination, withdrawal, or loss to follow-up prior to the end of the Week 24 visit window if they did not complete a Week 24 visit.

Applicable analysis sets (FAS, ECC, EPP, and STF) will include shared placebo participants from regimens A, B, C, and D. As RGE is the only regimen among the contributing regimens that is administered as an IV infusion, the ERO and ECM analysis sets are synonymous and only the ERO analysis set will be referenced. Similarly, the SRO and STN analysis sets are synonymous and only the SRO analysis set will be referenced.

6.2 Baseline Characteristics

The baseline characteristics summarized for participants randomized within RGE are the same as those specified in the M-SAP with the addition of ALSAQ-40 total and domain scores, CNS-BFS total score, King's stage, TRICALS score, weight, body mass index (BMI), serum creatinine concentration, serum NfL concentration, and baseline use of sodium phenylbutyrate/taurursodiol.

6.3 Primary Efficacy Analysis and Supportive Analyses

The primary analysis for RGE is a Bayesian shared-parameter, repeated-measures model of ALSFRS-R that accounts for loss of follow-up due to mortality. Details of the model, including documentation of operating characteristics under a range of scenarios, are provided in the MPRDR with the addition of baseline log-transformed serum NfL as a covariate. Baseline log-transformed serum NfL will be handled the same as previously specified covariates with respect to standardization, imputation of missing values, model for covariate effect, and prior distributions as described in Section 2.2.5 of the MPRDR. The Bayesian shared-parameter, repeated-measures model will be applied to the FAS analysis set as the primary analysis and to the ECC, ERO, EPP, and ERF analysis sets as sensitivity analyses.

The estimand of the primary analysis is the relative rate of disease progression (the "disease rate ratio" or DRR) of active treatment relative to placebo in the FAS population under an assumption that active treatment slows mean time to death or death equivalent by the same proportion as treatment slows the mean rate of functional progression as measured by change in ALSFRS-R total score over time. The estimand is defined by the following attributes:

- Treatment: weekly IV infusion of trehalose at a dosage of 0.75 g/kg vs. placebo.
- Population: FAS population as defined in Section 6.1.

- Variables: time to death or death equivalent and rate of change in ALSFRS-R total score from baseline to the Week 24 Visit.
- Intercurrent event 1: treatment discontinuation due to death or death equivalent: no ALSFRS-R data from participants who reach the death or death equivalent endpoint are included in the analysis, handled via mortality component in model, composite variable strategy approach.
- Intercurrent event 2: treatment discontinuation not due to death or death equivalent: handled via treatment policy approach, all data will be used including data collected during the placebo-controlled period after treatment discontinuation regardless of concomitant medication, for those participants who have not been censored due to mortality. Missing data post-treatment will not be imputed, handled via missing at random assumption.
- Population-level summary: mean ratio of hazard or progression rate of active treatment relative to placebo.

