#### Primary Efficacy Endpoint:

Change in disease severity as measured by the ALS Functional Rating Scale-Revised (ALSFRS-R) total score using a Bayesian repeated measures model that accounts for loss to follow-up due to mortality.

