5.7 Survival

The primary definition of survival time is the same as described in the M-SAP with the clarifications that PAV is defined as more than 22 hours per day of noninvasive or invasive mechanical ventilation for more than seven consecutive days, that time at risk should not be censored at date of consent withdrawal, and that time at risk should be censored at date last known alive. The date of PAV initiation, where applicable, will be imputed as the fifteenth day of a month if not specified more precisely. Any participant on PAV at baseline will be censored at baseline. A secondary survival endpoint of death alone, independent of any death equivalent (including a death equivalent that occurs prior to baseline), is also defined and will be censored at the Week 24 Visit if completed or at the earlier of the end of the Week 24 Visit window or date last known alive if a Week 24 visit is not completed. An exploratory survival endpoint of death or death-equivalent will censor at the earlier of last known PAV-free or last known alive.

Time at risk for the composite endpoint of death or death equivalent and time at risk for the endpoint of death alone will be measured from each participant's Baseline Visit. Time at risk will be censored at two time points: (1) at the Week 24 Visit as defined in the M-SAP, and (2) at a

Page 20 of 37

subsequent assessment of death or death equivalent scheduled approximately at the end of placebo-controlled follow-up of the last RGE participant. The primary analysis of survival will evaluate PAV-free survival to the Week 24 Visit time point.

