distributed with mean 0 and variance σ^2_r . The vector of residuals for a given participant are normally distributed with mean **0** and an unstructured covariance matrix **R**. The regimen-specific random effect for a given participant and residuals for that participant are uncorrelated.

The following SAS code specifies the model:

where id is a participant study identifier, trtrnd is the randomly assigned treatment group, visit is the visit identifier, Value is value of the efficacy endpoint being tested for a given participant at a given visit, sx2b1 is years since ALS symptom onset, dFRS is pre-baseline slope, rlz is an indicator of riluzole use at baseline, edv is an indicator of edaravone use at baseline, and NfL is baseline log-transformed serum NfL level. Covariates will be centered at their sample means. The primary estimate will be the treatment-dependent difference in change from baseline to the Week 24 Visit. The estimate and its 95% Wald confidence bounds will be obtained by a linear contrast of adjusted means. The following SAS code specifies the linear contrast for an endpoint measured every 8 weeks and assuming that the sort order for treatment group has the active group last and visits are sorted chronologically:

```
estimate "3|Act vs Plb|dWk 24" trtrnd*visit 1 0 0 -1 -1 0 0 1 / cl;
```

A significant difference in 24-week change from baseline in the direction of greater improvement or less worsening among participants randomized to active treatment would support inference of benefit from active treatment for the efficacy endpoint being tested.

The estimand estimated by the primary linear contrast of the repeated-measures linear mixed model is the mean difference in 24-week change from baseline of a given continuous efficacy endpoint in the active treatment group relative to the placebo group in the FAS. The estimand is defined by the following attributes:

- Treatment: weekly IV infusion of trehalose at a dosage of 0.75 g/kg vs. placebo.
- Population: FAS as defined in Section 6.1.
- Variables: absolute change in endpoint from baseline to the Week 24 Visit.
- Intercurrent event: treatment discontinuation: handled via a treatment policy approach, all data will be used including data collected during the placebo-controlled period after treatment discontinuation. Missing data post-treatment, including data missing due to death, will not be imputed, and will be handled via a missing at random assumption.

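### As written, SAP 6.3 and 6.5.2 discard every ALSFRS-R score, valid pre-event visits included, of any participant who dies or reaches PAV, while the MMRM keeps those visits

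*SAP*

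**What the plan says.** - **Primary analysis, SAP 6.3, intercurrent event 1 (death or death equivalent).** The rule is that "no ALSFRS-R data from participants who reach the death or death equivalent endpoint are included in the analysis". These participants are "handled via mortality component in model, composite variable strategy approach".
- **SAP 6.3, intercurrent event 2 (other treatment discontinuation).** All data are used, but only "for those participants who have not been censored due to mortality".
- **Death equivalent, SAP 5.7.** This is permanent assisted ventilation: "PAV is defined as more than 22 hours per day of noninvasive or invasive mechanical ventilation for more than seven consecutive days".
- **Model, SAP 6.3.** It is a "Bayesian shared-parameter, repeated-measures model of ALSFRS-R that accounts for loss of follow-up due to mortality", with one common effect on both components, "under an assumption that active treatment slows mean time to death or death equivalent by the same proportion". Protocol 2.1 describes the endpoint in similar terms, "using a Bayesian repeated measures model that accounts for loss to follow-up due to mortality". Neither description says that pre-event scores are removed.
- **CAFS, SAP 6.5.2 (first key secondary).** The exclusion is repeated. Pairs not ordered by survival are ranked on ALSFRS-R at the latest time when both members have an observation.
- **MMRM, SAP 6.5.3 (used for the second key secondary).** "Missing data post-treatment, including data missing due to death, will not be imputed". No participant is excluded.
- **Authority, SAP 1.** For primary-analysis specifications the MPRDR (4) ranks above the R-SAP (3). For other analyses, CAFS among them, the R-SAP ranks highest (5).

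**The concern.** Only scores after the event are undefined or hard to interpret. Someone who dies at Week 22 can have six valid scores before then (Baseline and Weeks 4, 8, 12, 16 and 20), and the sentence removes all six. Selection is then on a post-randomisation outcome and tends to remove fast progressors. If treatment changes mortality, the arms lose different shares of them, and the functional comparison shifts the wrong way: excess deaths on active make its decline look slower, and fewer deaths make it look faster.

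The text also sits badly with its neighbours. A model meant to account for loss to follow-up through mortality has no such loss left in its functional data once every score of a decedent is gone. The primary analysis and the MMRM would use different ALSFRS-R data with no reason given. SAP 7.1 asks an independent programmer to replicate the primary result; from this sentence that programmer could build a different dataset from the one the model report intends.

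**Working it through.** **Reading the text.** The exclusion in 6.3 has no time limit. A post-event-only reading would be empty for deaths, since no score follows a death; it would have content only for PAV. The restriction under intercurrent event 2 follows the same participant-level rule. So the plain reading drops pre-event visits.

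**Data lost.** The documents give no event rate. Assuming 5 to 12% by Week 24, of the 160 planned in the regimen: 0.05 × 160 = 8, and 0.12 × 160 = 19.2, so about 8 to 19 participants, before counting shared placebo participants.

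**Effect on the functional component.** The plan states no figure to reproduce, so this is an illustration. From the documents: ALSFRS-R at Weeks 0, 4, 8, 12, 16, 20 and 24 (SAP 2.9). Assumed: mean decline 1.0 point/month, slope SD 0.7, intercept SD 5.5, residual SD 1.5, control event rate 5, 8 or 12%, and hazard multiplied by 2 to 3 per SD of faster decline.

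- Slope of participant i: −(1.0 + 0.7u) × d, with u standard normal and d the true functional ratio (1 for control).
- Event hazard: λ × HR × exp(βu), with β from 0.7 to 1.1 and λ set to give the control event rate.
- Slopes are fitted by generalised least squares in 400,000 simulated participants per arm. Functional ratio R = active slope ÷ control slope; below 1 favours active.

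| Scenario | R, event participants dropped | R, pre-event visits kept |
|---|---|---|
| No functional effect, mortality HR 2 | 0.93–0.98 | 0.96–0.99 |
| No functional effect, mortality HR 0.5 | 1.01–1.04 | 1.01–1.03 |
| True 0.75 on both | 0.757–0.765 | 0.754–0.758 |
| No effect on either | 1.00 | 1.00 |

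Keeping the visits removes only part of the distortion when mortality alone differs.

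**Effect on a shared DRR.** The primary model estimates one ratio from both components. As a rough stand-in, the log functional ratio and log hazard ratio were pooled by inverse variance:

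log DRR = (w₁ log R + w₂ log HR) ÷ (w₁ + w₂), with w = 1/SE².

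This takes 120 active participants and an assumed 200 controls (the 40 in this regimen plus an assumed 160 shared).

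Hand check, 8% control events, HR 2, event participants dropped (R about 0.955, functional SE about 0.10):
- Active events: 120 × (1 − 0.92²) = 18.4. Control events: 200 × 0.08 = 16.
- SE of log HR = √(1/18.4 + 1/16) = 0.342, so w₂ = 8.55. For function, w₁ = 1/0.10² = 100.
- log DRR = (100 × (−0.0460) + 8.55 × 0.693) ÷ 108.55 = 0.012, so DRR = 1.01.
- SE = 1/√108.55 = 0.096.

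| Scenario | Pooled DRR, dropped | Pooled DRR, kept |
|---|---|---|
| No functional effect, HR 2 | 1.00–1.03 | 1.01–1.04 |
| No functional effect, HR 0.5 | 1.00–1.01 | 0.99–1.00 |
| True 0.75 on both | 0.755–0.766 | 0.752–0.760 |
| No effect on either | 1.00 | 1.00 |

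The rule moves the pooled value by about 0.01. The functional SE in these runs is about 0.09 to 0.12.

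**CAFS.** Take a decedent and someone last known alive before that death. Survival cannot order them, so function must. Under the repeated wording the decedent has no score at any visit, so no common time exists at which to rank the pair.

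**The case against.** The strongest reply is that the operative specification lies elsewhere. SAP 6.3 leaves the model's details to the MPRDR, which outranks the R-SAP here and is not supplied; 6.3 presents only the baseline NfL covariate as an addition, and Protocol 9.1 declares a single deviation from the default design (no early-success interims). The sentence may be a loose paraphrase of a likelihood that already uses pre-event visits. That stands. It is why nobody can assert from these documents what the model is actually fitted to.

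A reader might infer that the functional part is fitted to survivors only and that the primary result is therefore materially biased. The documents do not support this. Participants lost without an event still supply ALSFRS-R, so survivors can only mean those with no observed event. Event participants still inform the DRR through mortality, a declared composite strategy. The scenarios with the larger functional distortion also depart from the common proportional effect that 6.3 assumes.

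Other analyses give partial cover: the MMRM and random-slopes models state no such exclusion, and inverse probability weighting (6.5.8) and principal stratification (6.5.9) address loss due to death. But they are different models. The sensitivity analyses listed for the Bayesian model (ECC, ERO, EPP, ERF) change the analysis set, not this rule.

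The CAFS gap is narrow. Survival ranks first, and SAP 5.7 does not censor survival at withdrawal of consent, so only pairs with one member last known alive before the other's event are affected. No size can be given. There, however, the R-SAP is the top authority, so its wording governs.

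**Conclusion.** The point holds as a fault of specification: the stated rule removes valid data from the primary analysis and first key secondary, conflicts with the MMRM, and leaves some CAFS pairs without a ranking rule. It is a should-fix, not a must-fix. On the assumed inputs the effect on a roughly pooled DRR is about 0.01 against a standard error near 0.1, with no bias under a full null; when both components truly move by 0.75, the result shifts slightly towards no effect. A false slowing of 2 to 7% can be read off the functional ratio at HR 2, but it does not carry to the pooled DRR, because the mortality harm enters the same parameter, and keeping pre-event visits would itself leave a functional ratio of 0.96 to 0.99.

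These figures show direction and rough size only. Decline, SDs, event rates, hazard gradient and the 200 controls are assumptions. The simulation omits baseline covariates, and the pooling is not the Bayesian model.

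**What to change.** 1. In SAP 6.3 and 6.5.2, replace the exclusion with: *ALSFRS-R observations obtained before death or death equivalent are included; observations after it are not.*
2. Check 6.3 against the MPRDR before data lock. If the MPRDR already uses pre-event visits, the new sentence brings the SAP into line and nothing else changes.
3. If the MPRDR likelihood does omit event participants' function, keep the primary analysis as specified, say so plainly in 6.3 in place of the sentence in item 1, and add one named sensitivity run of the Bayesian model that retains pre-event visits.

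The cost is one sentence in two places and at most one further run of an existing model.

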6.4 Interim Analysis

RGE will be considered for early stopping for futility according to the interim analysis schedule and definition specified in the MPRDR. RGE will not be stopped early for success.

6.5 Secondary Efficacy Analyses

6.5.1 Hierarchical Testing

Primary inference for secondary efficacy endpoints will be based on analysis of the FAS. The primary CAFS analysis is described in Section 6.5.2. Primary estimates and inference for 24-week change of continuous endpoints will be by a mixed model repeated-measures analysis (see Section 6.5.3 below). Primary estimates and inference for time-to-event endpoints will be by Kaplan-Meier product-limit estimates and log-rank test (see Section 6.5.5 below). The sequence for testing secondary efficacy endpoints is the following:

- 1. CAFS using ALSFRS-R total score as the functional measure, freedom from death and PAV as the survival component, evaluated to the Week 24 time point, and adjusting the rank-sums for baseline covariates of pre-baseline slope of ALSFRS-R, time since symptom onset, use of edaravone, use of riluzole, and log-transformed serum NfL level,
- 2. Change from baseline to Week 24 in ALS functioning as assessed using ALSFRS-R total score change from baseline in the FAS,
- 3. Change from baseline to Week 24 in respiratory function as assessed by slow vital capacity (SVC) and measured as percent predicted using Global Lung Initiative normal values in the FAS,
- 4. Change from baseline to Week 24 in upper limb muscle strength as assessed isometrically using HHD and grip strength and measured as average percent change from baseline among maneuvers with non-zero strength at baseline in the FAS,
- 5. Change from baseline to Week 24 in lower limb muscle strength as assessed isometrically using HHD and measured as average percent change from baseline among maneuvers with non-zero strength at baseline in the FAS, and

Page 25 of 37

6. Survival defined as freedom from death and permanent assisted ventilation (PAV) from baseline to Week 24 in the FAS.

If the primary analysis indicates a significant slowing in disease progression, then each secondary efficacy endpoint in succession would be declared significant in the specified sequence using a comparison-wise criterion of two-tailed p < 0.05. After the first failure to declare significance, no endpoints lower in the hierarchy can be significant. This sequential closed-testing procedure controls the overall type 1 error rate at 5%. Nominal comparison-wise p-values for secondary efficacy endpoints will also be reported.

6.5.2 Combined Assessment of Function and Survival

The first key secondary analysis for RGE is a Combined Assessment of Function and Survival (CAFS). CAFS is a joint-rank test of a composite endpoint combining function as measured by change in ALSFRS-R total scores and survival as measured by time to death or death equivalent. CAFS will be applied to the FAS as the principal CAFS analysis with the addition of baseline log-transformed serum NfL level as a covariate (see MPRDR for more details) and to the ECC, ERO, and ERF analysis sets as sensitivity analyses.

The estimand is the stochastic probability that a randomly selected active participant will rank higher than a randomly selected placebo participant based on time to death or death equivalent or change from baseline in ALSFRS-R in the FAS. The estimand is defined by the following attributes:

- Treatment: weekly IV infusion of trehalose at a dosage of 0.75 g/kg vs. placebo.
- Population: FAS as defined in Section 6.1.
- Variables: the rank-sum score for each participant derived from comparing each study
 participant's outcome to all others in the analysis set in a series of pairwise comparisons,
 based on first on survival up to Week 24 and second on absolute change from baseline in
 ALSFRS-R total score.
- Intercurrent event 1: treatment discontinuation due to death or death equivalent: no ALSFRS-R data from participants who reach the death or death equivalent endpoint are included in the analysis, handled via mortality component in model, composite variable strategy approach.
- Intercurrent event 2: treatment discontinuation not due to death or death equivalent: handled via a treatment policy approach, all data will be used including data collected during the placebo-controlled period after treatment discontinuation regardless of concomitant medication, for those participants who have not been censored due to mortality. Pairs of participants will be ranked at the maximum follow-up time at which both participants have an observation during the placebo-controlled period. Missing data post-treatment will not be imputed and will be handled via a missing at random assumption.
- Population-level summary: the ANCOVA derived least-square mean rank-sum score for each treatment group, the LS mean estimated difference in rank-sum scores (adjusted for covariates: time since symptom onset, delta-FRS, baseline riluzole use, baseline edaravone use, and baseline log-transformed serum NfL) as well as the corresponding 2-sided p-value will be presented. A Gehan-Wilcoxon rank sum test will be performed for the FAS as a sensitivity analysis to the primary analysis.

Page 26 of 37

Inference from this analysis is supportive of inference from the Bayesian shared-parameter, repeated-measures model described in MPRDR.

Including the analysis above, all combinations of the following elements will be tested in separate joint-rank analyses:

- 1. Survival endpoint: (a) death or death-equivalent, and (b) death alone.
- 2. Function endpoint: (a) ALSFRS-R total score, and (b) SVC percent-predicted.
- 3. Analysis: (a) Wilcoxon rank-sum test by t-distribution approximation, and (b) adjusted mixed model or linear regression controlling for time since ALS symptom onset, delta-FRS, baseline log-transformed serum NfL level, use of riluzole at baseline, and use of edaravone at baseline, and including a random effect of regimen in all analyses that include at least three regimens or a fixed effect of regimen otherwise.

Additional CAFS analyses of long-term change in function and survival will be performed using ALSFRS-R total score and SVC percent-predicted as functional measures, freedom from death and PAV and freedom from death alone as survival components, both evaluated to the RCT LPLV time point and adjusting the rank-sums for baseline covariates of pre-baseline slope of ALSFRS-R, time since symptom onset, use of edaravone, use of riluzole, and log-transformed serum NfL level analyzed in the ERO analysis set.

